#### **8. Sources of Research Material:**

The electronic medical records of each enrolled patient will be accessed to obtain demographic data, laboratory values, echocardiogram reports, imaging reports, blood product transfusion requirements, and disposition. All study documents containing patient information will remain password protected. Only study personnel will have access to the study records.

### **9. Recruitment Methods and Consenting Process:**

Patients will be identified by the Children's Medical Center ECMO team. It is possible that potential subjects will be patients of the investigators. In that case where possible another member of the study team will approach the parent or guardians for consent. Parents or guardians will be approached by the study team within 24 hours of the start of ECMO.

If the patient is between 10 to 17 years old, we will obtain assent once sedation is removed and the patient is clinically able to give assent.

### **10. Potential Risks:**

Bivalirudin is rapidly cleaved by proteolytic enzymes creating a short half-life of 25 minutes. There is a theoretical increased risk of intracardiac thrombus development if the patient has stagnant blood flow due to poor cardiac output [19]. Daily echocardiograms will be performed to rule out intracardiac thrombus if there is clinical concern for stagnation of intracardiac blood flow including pulse pressure  $\leq$  10mmHg on arterial line or non-palpable pulses. Echocardiograms on patients in the bivalirudin arm that are performed to evaluate for intracardiac thrombus will not be charged to the patient. If the patient develops an intracardiac thrombus the patient will be changed to heparin infusion.

As noted previously, there is a potential risk of increased cost for the patient's in the bivalirudin group as bivalirudin is more expensive than heparin. A retrospective study comparing bivalirudin versus heparin noted that pediatric patients who received bivalirudin actually had decreased overall ECMO cost due to decreased number of blood product transfusions as compared to patients receiving UFH [2]. Like all anticoagulants, bivalirudin may cause unintended bleeding.

### **11. Subject Safety and Data Monitoring:**

Per current ECMO protocol all patients will be monitored closely for bleeding including intracranial hemorrhage. Neonates (patients aged 0 days to 28 days) will receive a head ultrasound every day for the first 3 days and thereafter per clinical discretion per current standard of care at CMC. All patients will receive a MRI after decannulation and prior to hospital discharge per current standard of care at CMC.

See DSMP for further information regarding data safety and monitoring.

### **12. Procedures to Maintain Confidentiality:**

Data will be stored in a password protected excel file with access granted only to study personnel.

### **13. Potential Benefits:**

This study has the potential to have a tremendous impact on the anticoagulation practice for all future neonatal and pediatric ECMO patients. Pending the results of this pilot study, we plan to develop and implement a multicenter study randomized control trial to confirm the benefits of bivalirudin. Improving ECMO anticoagulation is essential as the most common complications on ECMO are due to hemorrhage or thrombosis. Besides potentially devastating intracranial hemorrhage, ECMO patients are at risk for stroke, surgical site bleeding, cannula site bleeding, and exposure to multiple blood products. Improving anticoagulation could decrease these complications and significantly improve the outcomes of these critically ill children.

### **14. Biostatistics:**

Based on prior data from Ranucci et al in adult ECMO patients a sample size of approximately 10 in each arm (total 20 patients) will be sufficient to obtain statistical significance for the primary outcome. In this study we will use a variety of methods including tests of differences in means and medians, ANOVAS, correlations between changes of doses and changes in aPTT and multivariate ANOVAS and logistic regressions to analyze the impact of these treatments on a variety of patient outcomes such as time to goal aPTT, time in goal range of aPTT, ACT levels and changes, incidence of bleeding and clotting events, number of changes in dosage and other events, variations in aPTT level during treatment, time on ECMO, time in the ICU, ventilator days and mortality outcomes. Duration models will be used where appropriate.

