Bivalirudin has been used off label in children for deep venous thrombosis prophylaxis and treatment, cardiopulmonary bypass, cardiac catheterization and ECMO [17]. An open label study conducted by the manufacture of 110 neonatal and pediatric patients identified the dosing regimen, plasma concentration, and safety profile of bivalirudin. Bleeding occurred in 2 of 110 patients (1.8%) and thrombosis occurred in 8 of 110 patients (7.5%) [18]. At our institution, 6 non-ECMO neonatal and pediatric patients have been initiated on bivalirudin for concern of or confirmed heparin induced thrombocytopenia. In the six patients there were no thrombotic or hemorrhagic complications.

Pediatric ECMO studies using bivalirudin have thus far shown benefit and confirmed safety of bivalirudin but are limited to single case reports, one small case series, and one small retrospective study. Nagle et al described 12 neonatal and pediatric ECMO patients on bivalirudin and found no major bleeding events [1]. The study also defined the maintenance dose need to achieve goal aPTT. A combined pediatric and adult retrospective review compared 21 total patients using bivalirudin to UFH and found that patients receiving bivalirudin had decreased bleeding, decreased blood product transfusion, and decreased pediatric ECMO cost compared to patients receiving UFH [2]. An adult case-control study of 10 patients receiving UFH compared to 10 patients receiving bivalirudin, found that patients receiving bivalirudin had less variation of aPTT and a trend towards decreased number of changes of bivalirudin dose compared to patients receiving UFH [3]. No difference was seen in bleeding or thrombotic complications between the two groups [3]. To our knowledge, there is no prospective study comparing bivalirudin to UFH for pediatric or adult ECMO.

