### **3. Concise Summary of Project:**

We will prospectively enroll 30 neonatal and pediatric ECMO patients in the Pediatric Intensive Care Unit and Pediatric Cardiovascular Intensive Care Unit at Children's Medical Center, Dallas campus. The patients will be randomized into two arms; one arm will receive unfractionated heparin and the other arm will receive bivalirudin. There will be 15 patients in each arm for a total of 30 patients. We estimate that we will need to consent 50 patients to achieve our goal of 30 enrolled patients. Enrollment and completion of this study will require approximately two years.

After consent is obtained, patients will be randomized into either the unfractionated heparin group or bivalirudin group. The UFH group will be given UFH as is currently standard of care at Children's Medical Center. A bolus of UFH will be given on initiation and the UFH infusion will be titrated throughout the entire ECMO run based on combination testing of anti-factor Xa, aPTT, and thromboelastogram (TEG).

The bivalirudin group will receive an UFH bolus during cannulation and UFH infusion until consent obtained (maximum time of 24 hours) and then transitioned immediately from UFH infusion to bivalirudin infusion. Once initiated, the bivalirudin infusion will be titrated based on aPTT.

Bivalirudin's trade name is ANGIOMAX® and is manufactured by The Medicines Company. Bivalirudin directly inhibits thrombin by binding to the free and clot-bound thrombin. It is stored in a single-dose vial with 250 milligrams of bivalirudin to be reconstituted with sterile water. After reconstitution it may be stored at 2-8°C for up to 24 hours. It is excreted predominantly through proteolysis with 20% cleared renally. Patients with renal insufficiency or failure required a decrease in infusion rate based on creatinine clearance.

ECMO circuit tubing will be collected at time of circuit tubing change or at the end of ECMO. Normally, the used circuit tubing system is discarded in the appropriate biohazard waste container. For this study, will analyze the circuit tubing after it has been removed from the patient. After removal, the circuits will be drained and filled with normal saline (to prevent further clotting) by one of the ECMO team members or one of our study team members. The steps involved are detailed in the paragraphs below and will be covered by study finances and not billed to the patient in any way.

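### Does the undocumented basis for 10 patients per arm, with no primary test named, undermine a trial that enrols 15 per arm?

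*Combined protocol and SAP*

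**What the plan says.** The primary outcome (section 1) is the percentage of time at goal anticoagulation, compared between heparin and bivalirudin. Section 14 gives the whole sample-size argument in one sentence. It names a prior source in adult patients and concludes that "a sample size of approximately 10 in each arm (total 20 patients) will be sufficient to obtain statistical significance for the primary outcome". It then lists methods, beginning with "tests of differences in means and medians, ANOVAS", against a list of outcomes that includes time in the aPTT goal range. No method is tied to the primary outcome.

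The planned size is larger. Section 3 states: "There will be 15 patients in each arm for a total of 30 patients". Section 4 repeats it under Randomization. Neither section says why the figure rose from 10 to 15.

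Section 2 describes two earlier comparative studies:

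- **Reference 2**, which has the first author named in section 14: "A combined pediatric and adult retrospective review compared 21 total patients using bivalirudin to UFH". The finding reported is that "patients receiving bivalirudin had decreased bleeding, decreased blood product transfusion, and decreased pediatric ECMO cost compared to patients receiving UFH".
- **Reference 3**, by a different group: "An adult case-control study of 10 patients receiving UFH compared to 10 patients receiving bivalirudin". The bivalirudin patients "had less variation of aPTT and a trend towards decreased number of changes of bivalirudin dose".

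Section 13 calls the study a pilot, with a multicentre randomised trial planned to follow.

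**The concern.** Three things look wrong.

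1. **The source does not match its description.** Section 14 calls the prior data adult. Section 2 calls reference 2 mixed, with 21 patients. The adult study with 10 per group is reference 3. Neither is described as having measured percent time at goal.
2. **The figure cannot be reproduced.** With no difference, SD, alpha, power or test, a reader cannot see what effect the assurance presumes. Data on 20 or 21 patients are a thin basis for saying that a sample will be sufficient.
3. **The primary test is open.** If means and medians may both be tested, the conclusion could depend on a choice made after the data are seen.

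At stake is how the primary result is read. With 15 per arm, an observed benefit of 0.5 SD would not be significant. A reader who had been assured that 10 per arm was enough might take that as evidence of no benefit.

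**Working it through.** **Inputs.** From the documents: 10 per arm (section 14), 15 per arm (sections 3 and 4), 1:1 allocation, a continuous primary outcome. Assumed, because the documents do not give them: two-sided alpha 5%, 80% power, normal data, equal SDs, all patients evaluable, no crossover.

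**1. Reproducing the 10.** This cannot be done forwards, since every input is missing. It can only be solved backwards.

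**2. Difference implied by each size.** The standardised difference d solves: noncentral-t power(d, n per arm, 5% two-sided) = 0.80.

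- n = 10: d = 1.32 SD
- n = 15: d = 1.06 SD

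The ratio is 1.06 / 1.325 = 0.80. So 15 per arm keeps 80% power even if the effect presumed at 10 per arm is diluted by 20%.

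**3. Power actually in hand.** If 10 per arm gave 80% power, then d = 1.325 and power at 15 per arm is 94%. For smaller true effects, power at 15 per arm is 56% at 0.8 SD and 26% at 0.5 SD. The trial is therefore sized for a large effect, as its authors evidently expected.

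**4. Precision.** Expected 95% CI half-width at 15 per arm = t(0.975, 28 df) × √(2/15) = 2.048 × 0.365 = 0.75 SD. With an assumed SD of 20 points this is 15 points; with 30 points it is 22.

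**5. The misreading case.** For an observed difference of 0.5 SD, t = 0.5 / 0.365 = 1.37 on 28 df, p = 0.18, and the 95% CI is 0.5 ± 0.75, or −0.25 to 1.25 SD. An interval that wide shows plainly that a large benefit has not been excluded.

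**6. Choice between the t test and the rank-sum test.** Simulation of 200,000 trials per row, 15 per arm, normal data, pooled t test and exact rank-sum test (U ≤ 64):

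| True difference | t test significant | Rank-sum significant | Tests disagree |
|---|---|---|---|
| 0.5 SD | 26% | 24% | 6% |
| 0.8 SD | 56% | 52% | 8% |
| 1.06 SD | 80% | 76% | 6% |

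Under no difference, the two tests reject in 5.0% and 4.5% to 4.6% of trials. Declaring success if either rejects gives 5.7%.

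**7. The source.** Set side by side, sections 14 and 2 conflict on whether the population was adult or mixed. The explanation may be a wrong citation, or an adult subset of reference 2. The documents cannot settle which. Section 2 summarises each paper in a sentence or two, so its silence on time at goal shows what the protocol reports, not what the paper contains.

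**The case for a change.** The strongest case for a change is that pilot status excuses a small sample but not an assurance of significance, and that naming one primary method would cost a paragraph and no patients. The conflict over the source is visible within the protocol itself. If the prior data showed exactly 1.32 SD in 10 against 10, the 95% CI for the true effect would be 0.33 to 2.29 SD, and at the lower limit 15 per arm would have only 14% power. If the listed tests of medians were taken to mean the median test proper, it would disagree with the t test in 17%, 28% and 30% of trials at 0.5, 0.8 and 1.06 SD.

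The textual part stands: the citation mismatch, the missing assumptions, the unexplained step to 15 and the unnamed test are all there. The numerical part carries less weight. The interval starts from an observed effect that was itself solved back from an assumed power, so it is not evidence about the actual prior data. Most sample sizes taken from small studies would fail the same test. The median-test figures depend on a procedure the plan does not name, whose false-positive rate here is about 2.7% and whose power at 1.06 SD is about 52%. Few analysts would choose it for a continuous outcome with 15 per arm. Even if any of the three tests counted as success, the false-positive rate would be about 6.6%. Finally, nothing in the plan says that a non-significant result will be read as no benefit.

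**Conclusion.** No change is needed. The sample-size sentence is poorly documented and its reference does not agree with section 2, but no stated figure is shown to be false. The trial does not rest on 10 per arm. It enrols 15, a departure in the cautious direction, which turns 80% power into 94% for the same presumed effect. Rewriting the sentence would leave the same 30 patients compared between the same two arms.

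The open choice of test is a gap that ordinary practice fills. Percent time is bounded between 0 and 100, and statisticians reasonably differ on whether a t test or a rank test suits it at this size. Between those two, the choice alters significance in 6% to 8% of trials at the differences examined and adds about 0.7 percentage points to a 5% error rate. In a pilot that precedes a multicentre trial, that is a small matter.

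These sizes assume two-sided 5% testing, normal data with equal SDs, full evaluability and no crossover. Heavily skewed percentages could widen the disagreement between the tests, and true effects well below 1 SD would leave the trial with limited power whatever the sentence said. The conclusion covers only the sample-size basis and the choice of test, not how time at goal is defined in each arm.

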#### **4. Study Procedures:**

##### Unfractionated heparin group:

Patients in this group will receive UFH anticoagulation as is current standard of care at Children's. During cannulation a bolus dose of 50-100 units/kg of intravenous UFH will be given. A continuous UFH infusion based on age will be initiated once ACT is < 300 seconds. Infants less than one year will receive a starting dose of 28 units/kg/hour and children > 1 year will receive a starting dose of 20 units/kg/hour per current Children's protocol.

The UFH infusion will be titrated based on targeted anti-factor Xa, aPTT, and thromboelastogram. Labs will be drawn per current standard of care as noted below.

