##### aPTT and anti-factor Xa levels:

From time of cannulation until goal anticoagulation achieved: every 4-6 hrs

Once achieved goal: every 6 hours

Heparin dose change: 4 hours after change

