##### Bivalirudin group:

Patients in the bivalirudin group will initially receive UFH to allow for time for consent and randomization. During cannulation, an intravenous UFH bolus of 50-100 units/kg will be given. A continuous UFH infusion based on age will be initiated once ACT is < 300 seconds. Infants less than one year will receive a starting dose of 28 units/kg/hour and children > 1 year will receive a starting dose of 20 units/kg/hour. Once consent is obtained, the patients will be immediately transitioned from UFH to bivalirudin. The initial bivalirudin dose will be 0.15mg/kg/hr.

The bivalirudin infusion will be titrated via the nomogram below based on aPTT. Goal aPTT will be 1.5-2.5 times baseline. For patients with a normal aPTT prior to cannulation this translates to aPTT between 60-80 seconds.

Measured aPTT	Bivalirudin dose adjustment
< 45 seconds or < 16 seconds below target aPTT	Increase by 0.04 mg/kg/hr
45-59 seconds or 1-15 seconds below target aPTT	Increase by 0.02 mg/kg/hr
60-80 seconds or 1.5-2.5 times baseline aPTT	No change
81-95 seconds or 1-15 seconds above target aPTT	Decrease by 0.02 mg/kg/hr
>95 seconds or > 16 seconds above target aPTT	Decrease by 0.04 mg/kg/hr

For patients with renal insufficiency or failure, the initial bivalirudin dose will be adjusted based on creatinine clearance according to the nomogram below.

Creatinine Clearance (CrCl)	Initial infusion rate
> 60 ml/minute	0.15 mg/kg/hr
30-60 ml/minute	0.08 mg/kg/hr
< 30 ml/minute	0.05 mg/kg/hr
Dialysis dependent	0.02mg/kg/hr

aPTT labs:

From time of cannulation until goal anticoagulation achieved: every 2 hours

Once achieved goal: every 6 hours

Bivalirudin dose change: 2 hours after change

Other labs:

Daily TEG, PT/INR, d-dimer, fibrinogen, antithrombin, triglycerides, plasma free hemoglobin

Every 12 hour complete blood count

Every hour ACT

Blood product transfusion:

For both arms of the study patients, transfusion parameters will include: 15 ml/kg (maximum of 1 unit) of platelets for platelet count < 100 x 10^9, 1 unit/kg of cryoprecipitate for fibrinogen < 100 mg/dL, and 15 ml/kg (maximum of 1 unit) of packed red blood cells for hemoglobin < 8 -10 g/dL.

Cross over:

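### The number of dose changes is compared between arms with no exposure denominator, so it mixes titration stability with run length and, to a smaller degree, with the different recheck schedules.

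*Combined protocol and SAP*

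**What the plan says.** Section 14 of the combined protocol and SAP names several general methods: tests of means and medians, ANOVA, correlations and logistic regression. They are to be applied to a list of outcomes that includes "number of changes in dosage and other events, variations in aPTT level during treatment". Time on ECMO is a separate item in the same list. The section ends by allowing duration models where suitable, but does not link them to dose changes. By contrast, Section 3 (Concise Summary of Project) expresses transfusion per kilogram and ECMO day.

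Section 4 gives each arm its own laboratory schedule:

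- **After a dose change:** "Bivalirudin dose change: 2 hours after change" against "Heparin dose change: 4 hours after change".
- **Before goal:** "From time of cannulation until goal anticoagulation achieved: every 2 hours" for bivalirudin against "From time of cannulation until goal anticoagulation achieved: every 4-6 hrs" for UFH.
- **At goal:** the same instruction appears in both arms, "Once achieved goal: every 6 hours".

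The titration rules also differ. For bivalirudin, "The bivalirudin infusion will be titrated via the nomogram below based on aPTT". For heparin, "The UFH infusion will be titrated based on targeted anti-factor Xa, aPTT, and thromboelastogram", with no step table in this document.

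Under Research related costs, Section 4 also says that blood draws in both groups follow the centre's current protocol, apart from omitting anti-factor Xa in the bivalirudin group. That does not fit the different intervals above.

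**The concern.** A patient on ECMO for twice as long has, other things equal, twice as many opportunities for a dose change. Comparing counts over runs of unequal length therefore compares two things at once: how often the dose had to be altered per unit of time, and how long the patient was observed. Only the first describes stability of anticoagulation.

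If treatment shortens or lengthens runs, the count will differ even when the rate does not. If it does not affect run length, the spread of run lengths is still noise that hides a true difference in rate. The two recheck schedules add a second, smaller distortion, because the arm that is rechecked sooner has more occasions to change the dose.

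Section 2 (Background) cites an adult case-control study with a trend to fewer dose changes on bivalirudin. Section 13 says that a multicentre trial will follow depending on this pilot. A reader is likely to set the pilot's dose-change result beside that adult study, so it should be interpretable.

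**Working it through.** **The plan's own figure.** The plan gives no figure for dose changes. Section 14 says only that about 10 per arm suffices for the primary outcome. That cannot be reproduced, because no alpha, power, effect or SD is stated, and nothing below depends on it.

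**Inputs from the documents.** 15 patients per arm (Section 3). Recheck after a change at 2 h (bivalirudin) or 4 h (UFH). Checks before goal every 2 h or every 4-6 h, that is 12 a day against 4 to 6. Checks at goal every 6 h in both arms (Section 4).

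**Assumptions not in the documents.** Lognormal run length with median 7 days and log-SD 0.7 (range 0.4-0.8); 1.5 changes per day; between-patient CV of the rate 0.3 (range 0.3-0.5); Mann-Whitney test at two-sided 0.05.

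**Step 1: run length.** Expected count = rate × days on ECMO. At an equal rate, runs 1.5 times longer give 1.5 times the count. Chance alone can produce a sizeable gap. The SE of the difference in mean log run length is 0.7 × √(2/15) = 0.256, so a one-SE imbalance is a ratio of exp(0.256) = 1.29 in geometric mean run length.

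Share of simulated trials (3,000 per row) declared significant:

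| Scenario | Count | Per-day rate |
|---|---|---|
| No difference in rate or run length | 5.1% | 4.0% |
| Equal rate, runs 1.5 times longer in one arm | 23.4% | 4.1% |
| Equal rate, runs 2 times longer in one arm | 57.5% | 4.4% |
| True rate one third lower, equal run lengths | 23.2% | 55.9% |
| The same, run-length log-SD 0.5 | 32.1% | 57.6% |

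Over the ranges of log-SD and CV given above, the second row becomes about 17-46% against about 5%. Power for the one-third reduction becomes about 16-38% against 33-62%.

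**Step 2: schedule.** Let q be the share of checks that lead to a dose change, taken as equal in both arms. A check with a change is followed by the next one after 2 h or 4 h, and a check without a change after 6 h. Then:

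- bivalirudin changes per day = 24q / (2q + 6(1−q))
- UFH changes per day = 24q / (4q + 6(1−q))
- ratio = (6 − 2q) / (6 − 4q)

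| q | Bivalirudin per day | UFH per day | Ratio |
|---|---|---|---|
| 0.1 | 0.43 | 0.41 | 1.04 |
| 0.3 | 1.50 | 1.33 | 1.13 |
| 0.5 | 3.00 | 2.40 | 1.25 |
| 0.7 | 5.25 | 3.65 | 1.44 |
| 1.0 | 12.00 | 6.00 | 2.00 |

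A separate titration simulation used the bivalirudin step table in both arms and varied only the check schedule. It gave ratios of 1.06 to 1.23, within the range for q up to 0.5.

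**Step 3: does a per-day rate cure both problems?** It cures the first but not the second. With the schedule difference alone at q = 0.5 (3.0 against 2.4 a day), the rate flags a difference in 29% of trials and the raw count in 10%. The rate is more precise, so it also shows the schedule effect more clearly. That is why the result needs a caveat.

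**The case against.** The strongest reply has four parts.

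1. *The plan does not prescribe a raw count.* Section 14 is a loose list that neither states nor excludes adjustment for exposure. This stands as far as it goes. A raw count is the plain reading of an unqualified number, not an express rule. Still, choosing a rate is a concrete improvement and not just added detail.
2. *Randomisation balances run length.* This is correct in expectation: with equal run-length distributions the count keeps its error rate (5.1% simulated). False positives arise only if treatment changes run length. The loss of power remains either way, and a chance imbalance can still distort the estimate in this one trial.
3. *The stakes are low.* Dose changes are neither the primary outcome nor among the secondary outcomes in Section 1, and no aim concerns them. The sizes above also rest on assumed variation. Both points stand.
4. *The schedule effect works against bivalirudin.* It inflates the bivalirudin count, so alone it would not produce a spurious finding of fewer changes. This also stands.

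A reader might infer that bivalirudin is checked twice as often throughout, so that the count measures run length and schedule rather than stability. The documents do not support that. Once at goal both arms are checked every 6 h, and the twofold ratio is reached only if every check leads to a change. The count mixes the three influences.

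A reader might also infer that the share of checks followed by a change would be a clean replacement. It would not. It leaves the difference in titration rules in place, a check is not clearly defined for heparin titrated on three tests, and Section 8 does not list infusion-rate changes among the data collected. Nor does the lack of a heparin step table here show that none exists, since Section 4 defers to the centre's standard of care.

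**Conclusion.** The concern holds in a limited form. The dose-change comparison lacks an exposure denominator, and the plan already scales by exposure for transfusion. The main consequence is confounding with run length if treatment affects it, and in any case a loss of power, roughly from 33-62% down to 16-38% for a one-third reduction. The schedule contribution is smaller, about 4-25% more bivalirudin changes when up to half of checks lead to a change.

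The direction of these effects follows from the documents. Their size rests on assumed run-length spread, rate variation and an equal q in both arms. The primary outcome is not touched.

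**What to change.** In Section 14, replace the count with dose changes per patient-day on the assigned drug.

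- **Window:** from the start of the assigned drug after randomisation (for UFH patients already on heparin, from randomisation) until cross-over or end of ECMO. Exclude the heparin lead-in of up to 24 h in the bivalirudin arm.
- **Model:** an overdispersed count model, for example negative binomial, with log time on drug as offset. Report the rate ratio with its confidence interval.
- **Supporting measure:** the share of scheduled aPTT checks (bivalirudin) or aPTT/anti-factor Xa checks (UFH) followed by a dose change, if infusion-rate changes are captured.
- **Interpretation:** state that both measures describe drug plus titration protocol, because check intervals and titration rules differ by arm, and that the comparison is exploratory.
- **Consistency:** reconcile the statement on blood draws under Research related costs in Section 4 with the two laboratory schedules in the same section.

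The cost is a change of analysis wording and a little more analysis work. Dose-change times and time on drug must be extracted from the record. The change needs no additional patients or blood samples.
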